FDA	Food and Drug Administration
FPG	fasting plasma glucose
FPI	fasting plasma insulin
GCP	good clinical practice
GGT	gamma glutamyl transferase
GI	gastrointestinal
GLP	good laboratory practice
h	hour(s)
HbA1c	hemoglobin A1c (glycated hemoglobin)
HBsAG	hepatitis B surface antigen
HCV	hepatitis C virus
HDPE	high-density polyethylene
hERG	ether-à-go-go related gene
HIV	human immunodeficiency virus
HOMA-IR	homeostatic model assessment to quantify insulin resistance
HPF	high power field
HR	heart rate
IC ₅₀	half maximal inhibitory concentration
ICF	informed consent form
ICH	International Conference on Harmonisation
IRB	Institutional Review Board
ITT	intent to treat
IUD	intrauterine device
IWRS	interactive web response system
KDIGO	Kidney Disease: Improving Global Outcomes
kg	kilogram
kg/m ²	kilograms/meters squared (body mass index)
LDH	lactate dehydrogenase
L-NAME	L-nitroarginine methyl ester

Abbreviation	Term
LS	least square
m	minute
MAD	multiple ascending dose
MAP	mean arterial pressure
MCH	mean corpuscular hemoglobin
MCHC	mean corpuscular hemoglobin concentration
MCV	mean corpuscular volume
MedDRA	Medical Dictionary for Regulatory Activities
MEMS	Medication Event Monitoring System
mg	milligram
MI	myocardial infarction
mL	milliliter
mm Hg	millimeters of mercury
MMRM	mixed-effects model repeated measures
MPV	mean platelet volume
msec	millisecond
NO	nitric oxide
NT-proBNP	N-terminal pro B-type natriuretic peptide
NYHA	New York Heart Association
PEG	polyethylene glycol
pd	postdose
[REDACTED]	[REDACTED]
PDE	phosphodiesterase
[REDACTED]	[REDACTED]
[REDACTED]	[REDACTED]
PID	patient identification
PK	pharmacokinetic(s)
PKG	protein kinase G
PP	per protocol
PRN	pro re nata [ie, as needed]

Abbreviation	Term
PT	preferred term
QD	once daily
QTcF	QT interval corrected using Fridericia's formula
RAAS	renin-angiotensin-aldosterone system
SAE	serious adverse event
SBP	systolic blood pressure
Scr	serum creatinine
sGC	soluble guanylate cyclase
SOC	system organ class
tau	dosing interval
TEAE	treatment-emergent adverse event
UACR	urine albumin creatinine ratio

ELIGIBILITY CRITERIA

INCLUSION CRITERIA

Patients must meet all of the following criteria to be eligible for enrollment in this study:

1. Patient has signed an informed consent form (ICF) before any study-specific procedures are performed.
2. Patient is an ambulatory male or female from 25 to 75 years old at the Screening Visit.
3. Patient has type 2 diabetes diagnosed by a physician or nurse practitioner ≥ 6 months before the Screening Visit, has been on ≥ 1 antihyperglycemic medication for ≥ 12 weeks preceding the Randomization Visit, and has been on a stable regimen (ie, same drug and same dose) of ≥ 1 antihyperglycemic medication for ≥ 28 days preceding the Randomization Visit.
(Modification of short-acting insulin throughout the Screening Period will not affect eligibility.)
4. Patient has been on a stable regimen (ie, same drug and dose) of an angiotensin-converting enzyme inhibitor (ACEi) or an angiotensin receptor blocker (ARB), for ≥ 28 days preceding the Randomization Visit and is expected to remain on their regimen through the Follow-up Visit. (Note: These medications may be modified during the study if medically necessary.)
5. If patient is on medications for hypertension, regimen (drug[s] and dose[s]) must be stable for ≥ 28 days preceding the Randomization Visit and is expected to remain stable through the Follow-up Visit. (Note: Medications for antihypertension may be modified during the study if medically necessary.)
6. Patient has the following:
 - a. Estimated glomerular filtration rate (eGFR) 30 to 75 mL/min/1.73 m² by the Chronic Kidney Disease Epidemiology Collaboration (CKD-EPI) creatinine equation (1) at the Screening and Baseline Visits
 - b. Urine albumin creatinine ratio (UACR) >200 mg/g and <5000 mg/g at the Screening and Baseline Visits (at the Baseline Visit, the mean of the 2 first morning void tests will be used to determine eligibility)
 - c. Serum albumin >3.0 g/dL at the Screening and Baseline Visits
 - d. Hemoglobin A1c (HbA1c) $\leq 12\%$ at the Screening and Baseline Visits
 - e. Systolic blood pressure (BP) of 110 to 160 mm Hg based on the average of 3 seated automated office blood pressure (AOBP) measurements at the Screening and Baseline Visits
7. Female patient must be postmenopausal (no menses for ≥ 12 consecutive months); surgically sterile (ie, bilateral oophorectomy, hysterectomy, or tubal sterilization [tie, clip, band, or burn]); must agree to completely abstain from heterosexual intercourse; or, if heterosexually

active, must agree to use 1 of the following methods of birth control from the date she signs the ICF until 60 days after the final dose of study drug:

- a. Progesterone implant or an intrauterine device (IUD)
- b. Combination of 2 highly effective birth control methods (eg, diaphragm with spermicide plus a condom, condom with spermicide plus a diaphragm or cervical cap, hormonal contraceptive [eg, oral and transdermal patch] plus a barrier method, partner with vasectomy [conducted \geq 60 days before the Screening Visit or confirmed via sperm analysis] plus a hormone/barrier method).
8. Male patients must be surgically sterile by vasectomy (conducted \geq 60 days before the Screening Visit or confirmed via sperm analysis), must agree to completely abstain from heterosexual intercourse, or, if heterosexually active, must agree to use a combination of 2 highly effective birth control methods (eg, condom with spermicide plus partner IUD, condom with spermicide plus a partner diaphragm or cervical cap, partner hormonal contraceptive [including progesterone implant] plus a barrier method, or postmenopausal partner [no menses for \geq 1 year or 12 consecutive months] plus barrier method) from the Screening Visit through 60 days after the final dose of study drug.
9. Patient must agree not to make any major lifestyle (eg, diet, exercise) changes from the Screening Visit through the Follow-up Visit.

EXCLUSION CRITERIA

Patients who meet any of the following criteria will not be eligible to participate in the study:

1. Patient has a history of secondary hypertension (ie, renal artery stenosis, primary aldosteronism, or pheochromocytoma).
2. Patient has a body mass index (BMI) <20 or $>45 \text{ kg/m}^2$ at the Screening Visit.
3. Patient has elevated ($>1.5 \times$ the upper limit of normal as defined by laboratory) levels of alanine aminotransferase (ALT) or aspartate aminotransferase (AST) at the Screening or Baseline Visits.
4. Patient has hemoglobin level $<9 \text{ g/dL}$ at the Screening or Baseline Visit.
5. Patient has a 12-lead electrocardiogram (ECG) demonstrating severe bradycardia (heart rate <50 beats per minute) or QTcF is ≥ 450 msec for male patients or is ≥ 470 msec for female patients at the Screening or Baseline Visit. (NOTE: If on initial ECG, QTcF exceeds the limit, the ECG will be repeated 2 more times, and the average of the 3 QTcF values will be used to determine the patient's eligibility at the Screening and Baseline Visits.)

6. Patient has any history of platelet dysfunction, hemophilia, von Willebrand disease, coagulation disorder, other bleeding diathesis, or significant, nontraumatic bleeding episodes, such as from a gastrointestinal (GI) source.
7. Patient has hepatic impairment defined as Child-Pugh A, B, C.
8. Patient has significant comorbidities (eg, malignancy, advanced liver disease, pulmonary hypertension, pulmonary fibrosis, lung disease requiring supplemental oxygen) or other significant conditions, including clinically significant abnormality(ies) in laboratory values, that, in the Investigator's opinion, would limit the patient's ability to complete or participate in this clinical study; has been hospitalized for cardiovascular, renal, or metabolic cause in the 3 months before the Screening Visit; or has a life expectancy of less than 1 year.
9. Patient has a history of a chronic GI disease, which in the Investigator's opinion could cause significant GI malabsorption.
10. Patient with known nondiabetic renal disease (eg, known polycystic kidney disease, focal segmental glomerulosclerosis) or nondiabetic etiology of renal function compromise. Concomitant hypertension-associated nephrosclerosis superimposed on diabetic nephropathy is acceptable.
11. Patient has had prior dialysis, renal transplant, or planned renal transplant. (Prior dialysis does not include transient, short-term dialysis indicated for an illness or during acute hospitalization. This "transient" dialysis must have occurred >3 months prior to Randomization, must have been <7 days in duration, and the current eGFR must be stable and within the eligible range [$>30 \text{ mL/min/1.73 m}^2$].)
12. Patient has clinically active, symptomatic, or unstable coronary artery or heart disease within the 3 months before the Screening Visit, defined as 1 of the following:
 - a. Hospitalization for myocardial infarction (MI), unstable angina, or heart failure
 - b. New-onset angina with positive functional study or coronary angiogram revealing stenosis
 - c. Coronary revascularization procedure
13. Patient has a documented history of New York Heart Association (NYHA) Class III or IV heart failure.⁽²⁾ A prior brief/transient NYHA Class III or IV designation is not exclusionary provided that, at Randomization, the status is Class II or better and has been stable without deterioration into a more severe class for ≥ 3 months.
14. Patient has a positive hepatitis panel (hepatitis B surface antigen [HBsAg] and antihepatitis C virus [HCV]) or human immunodeficiency virus (HIV) antibody at the Screening Visit.
15. Patient has a history of viral or bacterial infection within 4 weeks of the Screening Visit.
16. Patient has had surgery with general anesthesia in the 12 weeks before the Screening Visit or has scheduled or planned surgery with general anesthesia during the study.

17. Patient has a history of active alcoholism or drug addiction during the year before the Screening Visit or, at the Screening Visit, has a positive drug screen for drugs not legally prescribed.
18. Patient is taking specific inhibitors of phosphodiesterase 5 (PDE5), nonspecific inhibitors of PDE5 (including dipyridamole and theophylline), any supplements for the treatment of erectile dysfunction, riociguat, or nitrates or nitric oxide (NO) donors in any form. These medications and supplements are prohibited from 7 days before Randomization through the duration of the study.
Patient is taking strong cytochrome P450 3A (CYP3A) inhibitors, examples of which include azole antifungals, macrolide antibiotics, protease inhibitors, and diltiazem. These medications and excessive grapefruit intake are prohibited 14 days before Randomization through the duration of the trial.
See [Appendix 1](#) for a more detailed list of prohibited medications and supplements.
19. Female patient who may wish to become pregnant and/or plan to undergo egg donation or egg harvesting for current or future in vitro fertilization during the study and for at least 60 days after the final dose of study drug.
20. Male patient unwilling to refrain from sperm donation during the study and for at least 60 days after the final dose of study drug.
21. Patient has a history of clinically significant hypersensitivity or allergies to any of the inactive ingredients contained in the active or placebo drug products.
22. Patient has previously received IW-1973 in a study, or received an investigational drug during the 30 days or 5 half-lives of that investigational drug (whichever is longer) before the Screening Visit, or is planning to receive another investigational drug at any time during the study.
23. Female patient is pregnant or nursing at the Screening Visit. Nursing is not allowed from the Screening Visit through the Follow-up Visit.
24. Patient will not be able to adhere to the trial assessment schedule, or, in the clinical judgment of the Investigator, the patient is otherwise not suitable for the trial.

Note: Screening Visit assessments may take place over more than 1 day. Patients may be rescreened should they discontinue in the Screening Period due to visit window deviations or other administrative reasons. In addition, laboratory values or BPs that are outside the range specified in the protocol may be repeated to confirm eligibility during the Screening Period at the Investigator's discretion after consultation with the Medical Monitor.

SCHEDULE OF EVENTS

Visit Days → Study Procedure ↓	Screening Period			Treatment Period			Follow-up Period Follow-up Visit (Day 115 ±3)
	Screening Visit (Day -45 to -15)	Baseline Visit (Day -7 ±3)	Randomization Visit (Day 1)	Week 1 Visit (Day 8 ±1)	Week 4 Visit (Day 29 ±3)	Week 8 Visit (Day 57 ±3)	
ICF signed	X						
Demographics	X						
Medical history	X						
Prior & concomitant meds	X	X	X	X	X	X	X
Inclusion/exclusion evaluation/review	X	X	X				
Physical exam	X					X	
Hepatitis (HBsAg, HCV) & HIV screen	X						
Drug screen (a)	X						
Urine pregnancy test (b)	X	X	predose	predose	predose	predose	X
Weight (W) & height (H)	W, H	W	W	W	W	W	W
12-lead ECG (c)	X	X					predose
Respiratory rate and oral temperature	X		pre: 0 (\leq 30m) pd: 1h (\pm 15m)	pre: 0 (\leq 30m) pd: 1h (\pm 15m)			X
Seated pulse and BP (d)	X	X					X
First-void urine for UACR (e)	X	preVisit	preVisit	preVisit	preVisit	preVisit	preVisit
Issue UACR sample supplies	X	X	X	X	X	X	
Urinalysis sample (f)	X	X					predose
Serum chemistry, coagulation, hematology (f)	X	X	serum creatinine & glucose only pre: 0 (\leq 30m)	serum creatinine & glucose only pre: 0 (\leq 30m)	serum creatinine & glucose only pre: 0 (\leq 30m)	serum creatinine & glucose only pre: 0 (\leq 30m)	X
Hemoglobin A1c (f)	X	X	X	X	pre: 0 (\leq 30m)	pre: 0 (\leq 30m)	X
Adverse event evaluations	X	X	X	X	X	X	X

Visit Days → Study Procedure ↓	Screening Period			Treatment Period				Follow-up Period
	Screening Visit (Day -45 to -15)	Baseline Visit (Day -7 ±3)	Randomization Visit (Day 1)	Week 1 Visit (Day 8 ±1)	Week 4 Visit (Day 29 ±3)	Week 8 Visit (Day 57 ±3)	End of Treatment Visit (Day 87 ±3)	
Fasting plasma glucose & insulin (f)		X		pre: 0 ($\leq 30m$)	pre: 0 ($\leq 30m$)	pre: 0 ($\leq 30m$)	pre: 0 ($\leq 30m$)	pre: 0 ($\leq 30m$)
Urine cotinine			predose					
24- or 12-h ABPM (h)		X (24h)	X		X (12h)	X (12h)	X (24h)	
Return of ABPM monitor						X	X	X
Orthostatic (seated to standing) pulse and BP (i)			pre: 0 ($\leq 30m$) pd: 1,2,4,6h ($\pm 15m$)	pre: 0 ($\leq 30m$) pd: 1,2,4,6h ($\pm 15m$)	pre: 0 ($\leq 30m$)	pre: 0 ($\leq 30m$)	pre: 0 ($\leq 30m$)	X
Randomization			X					
MEMS instruction/review			X	X	X	X	X	
Study drug dispensed			X		X	X		
In-clinic study drug administration (j)			X	X	X	X	X	
Study drug return (k)				X	X	X	X	
Pharmacokinetic blood samples			pre: 0 ($\leq 30m$) pd: 1,3,6h ($\pm 15m$)	pre: 0 ($\leq 30m$) pd: 1,3,6h ($\pm 15m$)	pre: 0 ($\leq 30m$)	pre: 0 ($\leq 30m$)	pre: 0 ($\leq 30m$) pd: 3h ($\pm 15m$)	X
Study completion								X

ABPM=ambulatory blood pressure monitoring; automated office blood pressure (AOBP); BP=blood pressure; cGMP=cyclic guanosine monophosphate; ECG=electrocardiogram; [REDACTED]; h=hour(s); H=height; HBsAg=hepatitis B surface antigen; HCV=hepatitis C virus; HIV=human immunodeficiency virus; [REDACTED]

ICF=informed consent form; KDOQI-SF=Kidney Disease Outcomes Quality of Life—Short Form; m=minute(s); MEMS=Medication Event Monitoring System; pd=postdose; [REDACTED]

UACR=urine albumin creatinine ratio; W=weight pre=predose; [REDACTED]

- a. Urine drug screen for selected drugs of abuse
- b. For female patients, a negative pregnancy test (by urine dipstick) must be documented at all study visits and confirmed negative before dosing when applicable. Female patients who are postmenopausal (no menses for ≥ 12 consecutive months) or surgically sterile (ie, bilateral oophorectomy, hysterectomy, or tubal sterilization [tie, clip, band, or burn]) do not have to have a urine pregnancy test. Patients should be reminded of birth control requirements.
- c. Patients must be supine for ≥ 5 m before the ECG recording (Note: If on initial ECG, QTcF is ≥ 450 msec for male patients or is ≥ 470 msec for female patients, the ECG will be repeated 2 more times, and the average of the 3 QTcF values will be used to determine the patient's eligibility).
- d. Seated BP will be the average of 3 measurements obtained by AOBP at 2-m intervals after the patient has been sitting quietly for ≥ 5 m.
- e. At the Screening Visit, single urine sample, which may not be first void; thereafter, 2 first-void urine samples collected on the 2 consecutive mornings before each scheduled visit. Patients will be supplied with specimen collection supplies at the preceding study visit. [REDACTED]
- f. Except for the Screening Visit, patients must fast for ≥ 8 h before predose sample collection. [REDACTED]
- g. [REDACTED]
- h. Patients will begin using the ABPM monitor at the clinic visit before dosing, where applicable, will wear it for ≥ 12 or 24 h, and will return the monitor to the clinic. Baseline Visit: At least 65% patient compliance is preferred, with no more than 10 missed readings during the day (7 am – 10 pm) and/or 3 missed readings at night (10:30 pm – 6:30 am), and no more than 6 missed readings in succession. (If the ABPM assessment does not meet these criteria, the medical monitor must be contacted PRIOR to randomizing the subject.)
- i. Patient must sit quietly for ≥ 5 m before seated BP and pulse measurements are taken. At End of Treatment Visit, seated predose BP will be the average of 3 measurements. When applicable, BP and pulse measurements will be obtained before blood draws and before study drug administration.
- j. Study drug will be administered in the clinic on study visit days after predose assessments (Day 1, morning dose only). Patients should take study drug with water, may take with or without food, and for QD dosing (Week 1 Visit onward), may swallow 2 tablets together.
- k. At the Week 1 Visit, patients will bring the study drug bottles dispensed on Day 1 to the clinic. MEMSCaps will be read, and the subject will be administered their Day 8 (± 1) study drug dose in the clinic from the Day 1 bottles. The subject will continue to dose from the Day 1 bottles until they return for the Week 4 Visit.

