Screening Period: The Screening Period will begin with the signature of the informed consent form (ICF) at the Screening Visit and may last up to 45 days. At the Screening Visit (which can occur from Day -45 to Day -15), patients will undergo preliminary screening procedures to determine their eligibility. Eligible patients will return to the clinic for the Baseline Visit (Day 7 ± 3) for baseline and eligibility assessments including 24-hour ambulatory blood pressure monitoring (ABPM). The end of the Screening Period will coincide with the beginning of the Treatment Period.

Treatment Period: The Treatment Period will begin on Day 1 at Randomization (there is no Day 0) and will end after the End of Treatment Visit on Day 87 (± 3). Patients will be stratified by baseline eGFR (ie, eGFR 30 to 45, >45 to 60, and >60 to 75 mL/min/1.73 m²) and randomized in a 1:1:1 ratio to receive 20 mg IW-1973, 40 mg IW-1973, or placebo for approximately 12 weeks.

Dosing on Days 1 to 7 (± 1) will be BID (twice daily), morning and evening; dosing on Day 8 (± 1) onward will be QD (once daily), 2 tablets in the morning.

[figure not shown]
At the Randomization Visit on Day 1, patients will receive their morning dose of study drug in the clinic and will undergo safety, efficacy, and pharmacokinetic (PK) assessments, including blood and urine collections at prespecified times ([Schedule of Events](#)). Patients must stay in the clinic at least 6 hours postdose and may leave the clinic at the Investigator's discretion following all study procedures.

At the Week 1 Visit on Day 8 (± 1), patients will return to the clinic and receive their first QD dose of study drug in the clinic. Patients will undergo safety, efficacy, and PK assessments, including blood and urine collections at prespecified times (see [Schedule of Events](#)). Patients must stay in the clinic at least 6 hours postdose and may leave the clinic at the Investigator's discretion following all study procedures.

At the Week 4 (Day 29 ± 3), Week 8 (Day 57 ± 3), and End of Treatment (Day 87 ± 3) Visits, patients will return to the clinic for study drug administration; safety, efficacy, and PK assessments; and study drug supply, if applicable (see [Schedule of Events](#)).

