3. INVESTIGATIONAL PLAN

3.1 OVERALL STUDY DESIGN AND PLAN

This Phase 2, multicenter, randomized, double-blind, placebo-controlled, parallel-group study will evaluate 2 dose levels of IW-1973 compared with placebo. The study will enroll approximately 150 patients with type 2 diabetes mellitus and albuminuria who are on a steady regimen of a RAAS inhibitor, such as an ACEi or an ARB (see [Eligibility Criteria](#)). Patients will be stratified by baseline eGFR (ie, eGFR 30 to 45, >45 to 60, and >60 to 75 mL/min/1.73 m²) and randomized in a 1:1:1 ratio to receive daily 20 mg IW-1973 Tablets, 40 mg IW-1973 Tablets, or placebo tablets for daily for approximately 12 weeks.

Each patient will progress through 3 distinct study periods ([Figure 1](#)).

Figure 1. Study Schematic

Screening Period: The Screening Period will begin with the signature of the informed consent form (ICF) at the Screening Visit and may last up to 45 days. At the Screening Visit (which can occur from Day -45 to Day -15), patients will undergo preliminary screening procedures to determine their eligibility. Eligible patients will return to the clinic for the Baseline Visit (Day -7 ± 3) for baseline and eligibility assessments including 24-hour ambulatory blood pressure

monitoring (ABPM). The end of the Screening Period will coincide with the beginning of the Treatment Period.

Treatment Period: The Treatment Period will begin on Day 1 at Randomization and will end after the End of Treatment Visit on Day 87 (± 3). Patients will be stratified by baseline eGFR (ie, eGFR 30 to 45, >45 to 60, and >60 to 75 mL/min/1.73 m²) and randomized in a 1:1:1 ratio to receive daily 20 mg IW-1973, 40 mg IW-1973, or placebo daily for approximately 12 weeks; each daily dose will comprise 2 tablets. Dosing on Days 1 to 7 (± 1) will be BID (twice daily), 1 tablet in the morning and 1 tablet approximately 12 hours later in the evening; dosing on Day 8 (± 1) onward will be QD (once daily), 2 tablets in the morning.

At the Randomization Visit on Day 1, patients will receive their morning dose of study drug in the clinic and will undergo safety, efficacy, and PK assessments, including blood and urine collections at prespecified times (see [Schedule of Events](#)). Patients must stay in the clinic at least 6 hours postdose and may leave the clinic at the Investigator's discretion following all study procedures.

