3.8.6 Hemodynamics

Hemodynamic assessments will include seated BP and pulse, orthostatic (seated-to-standing) BP and pulse, and ABPM. Outside of the ABPM assessments, all other BP and pulse measurements will be taken by automated office blood pressure (AOBP); manual measurements are allowed in cases in which an AOBP machine malfunctions or is not available.

Blood pressure and pulse measurements at the Screening and Baseline Visits will be performed with patients in the seated position. Seated BPs for study eligibility will be the average of 3 measurements obtained at 2-minute intervals after the patient has been sitting quietly for at least 5 minutes.

Blood pressure and pulse measurements at the Randomization, Week 4, Week 8, End of Treatment, and Follow-up Visits will be seated-to-standing for calculation of orthostatic BP and pulse. Patients should sit quietly for at least 5 minutes before seated measurements are taken, and then assume a standing position for 30 to 60 seconds before standing measurements are taken. At the End of Treatment visit, seated predose BP will be the average of 3 measurements.

When applicable, BP and pulse measurements should be taken before blood draws. All predose BP and pulse measurements should be taken before all oral and any antihypertensive concomitant medications.

Patients will begin 24-hour ABPM at the study site during the Baseline and End of Treatment Visits and will begin 12-hour ABPM at the study site during the Week 4 and Week 8 Visits. Patients will return the ABPM equipment to the study site at the following study visit.

Baseline Visit ABPM assessment: At least 65% compliance is preferred, with no more than 10 missed readings during the day (7 am – 10 pm) and/or 3 missed readings at night (10:30 pm – 6:30 am), and no more than 6 missed readings in succession. (If a patient's ABPM assessment does not meet these criteria, the medical monitor must be contacted PRIOR to randomizing the patient.)

At the Week 4, Week 8, and End of Treatment Visits, ABPM should begin before study drug administration.

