APPENDIX 1 PROHIBITED MEDICINES AND SUPPLEMENTS

Prohibited from 7 days before Randomization (Day 1) through the duration of the study

- Specific inhibitors of PDE5, including sildenafil, tadalafil, vardenafil
- All supplements for the treatment of erectile dysfunction
- Nonspecific inhibitors of PDE5, including dipyridamole, theophylline
- Other sGC stimulators, including riociguat
- Nitrates including nitroglycerin, isosorbide mononitrate, isosorbide dinitrate, sodium nitroprusside, amyl nitrate
- Other NO donors in any form, including beetroot

Prohibited from 14 days before Randomization (Day 1) through the duration of the study

- Strong inhibitors of CYP3A, including azole antifungals (eg, itraconazole, posaconazole), conivaptan, diltiazem, idelalisib, macrolide antibiotics (eg, clarithromycin, telithromycin), nefazodone, protease inhibitors (eg, ritonavir, boceprevir), and excessive grapefruit intake or concentrated grapefruit supplements

CYP=cytochrome P450; NO=nitric oxide; PDE=phosphodiesterase

APPENDIX 2

APPENDIX 3

APPENDIX 4

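### Three of the seven permitted Baseline Visit days fall before the 7-day prohibition on same-pathway drugs opens, so the only pretreatment 24-hour ABPM and the final eligibility seated BP can be recorded on such a drug

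*Protocol*

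**What the plan says.** Three places in the protocol set the drug window. Exclusion Criterion 18 covers specific and nonspecific PDE5 inhibitors, erectile-dysfunction supplements, riociguat, and nitrates or nitric oxide donors: "These medications and supplements are prohibited from 7 days before Randomization through the duration of the study". Section 3.6.1 repeats this, and Appendix 1 heads its list "Prohibited from 7 days before Randomization (Day 1) through the duration of the study". Criterion 18 itself, however, begins in the present tense with no date: it excludes a patient who is taking one of these products. Eligibility is reviewed at the Screening, Baseline and Randomization Visits (Schedule of Events; sections 3.9.1.1, 3.9.1.2 and 3.9.2.1).

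On the measurements, section 3.1 has patients return for the "Baseline Visit (Day -7 ± 3) for baseline and eligibility assessments including 24-hour ambulatory blood pressure" monitoring. Section 3.8.6 adds: "Patients will begin 24-hour ABPM at the study site during the Baseline and End of Treatment Visits". The remaining recordings are 12-hour ones at Weeks 4 and 8. Inclusion Criterion 6e judges the 110 to 160 mm Hg systolic limits on the average of three seated readings at Screening and at Baseline. Section 3.9.2.1 (Randomization) lists return of the ABPM monitor, two further first-void urine samples and a predose seated-to-standing BP.

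**The concern.** The prohibition is counted back from Randomization, whereas the baseline ABPM and the last eligibility BP are taken up to 10 days before it. The listed drugs act on the NO-sGC-cGMP pathway that section 1.2 links to relaxation of vascular smooth muscle, and that is also the study drug's pathway. If such a drug is on board at the Baseline Visit and then withdrawn, the baseline pressure is lowered by something absent from the on-study readings. The within-arm fall in BP is then understated, and the systolic eligibility limits are applied to a pressure that the patient will not carry into the treatment period.

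Section 3.2 names hemodynamic measures, alongside UACR, among the things that 12 weeks of treatment should show. ABPM is the exposed measurement because no second pretreatment recording is scheduled to replace an affected one.

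**Working it through.** **Inputs**
- Drug window: from 7 days before Randomization (Exclusion 18, section 3.6.1, Appendix 1).
- Day numbering: Randomization is Day 1 and "there is no Day 0" (synopsis, Treatment Period), so Day -k is k days before Day 1. This convention reproduces the protocol's maximum participation: Screening on Day -45 and Follow-up on Day 115 + 3 = 118 give 45 + 118 = 163 days, as section 3.3 states.
- Baseline Visit: Day -7 ± 3, that is Day -10 to Day -4 (sections 3.1 and 3.9.1.2; the synopsis prints the day without its minus sign).
- Urine samples: the two mornings before each visit (section 3.8.8.3).

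**Day count.** A measurement precedes the window if it is taken more than 7 days before Day 1.

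| Baseline Visit | ABPM start and seated BP | Baseline Visit urines |
|---|---|---|
| Day -10 | before window | Day -12, -11: both before |
| Day -9 | before window | Day -11, -10: both before |
| Day -8 | before window | Day -10, -9: both before |
| Day -7 | boundary | Day -9, -8: both before |
| Day -6 | inside | Day -8, -7: one before |
| Day -5 | inside | Day -7, -6: neither before |
| Day -4 | inside | Day -6, -5: neither before |

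For ABPM and seated BP, 3 of 7 permitted days precede the window, by at most 10 - 7 = 3 days. By contrast, the window for strong CYP3A inhibitors ("These medications and excessive grapefruit intake are prohibited 14 days before Randomization through the duration of the trial") opens on Day -14 and so covers every Baseline Visit measurement, the earliest being Day -12.

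**What is measured again.** The Randomization Visit urines are from Day -2 and Day -1, and its predose BP is from Day 1. All lie inside the 7-day window. ABPM is not repeated.

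**Scale for the primary endpoint.** First the plan's own figure: power = Φ(δ/(SD·√(2/n)) - 1.645) with δ = 0.376, SD = 0.67 and n = 40 gives Φ(2.510 - 1.645) = 80.6%, matching the stated 80% or so.

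Now suppose, against the day count above, that affected urines did serve as the analysis baseline. Let a share p of patients carry a baseline offset a on the log scale. Then SD² = 0.67² + p(1 - p)a². The documents give neither p nor a. Over the assumed ranges p = 2% to 10% and a = 0.1 to 0.3, the worst case is SD = √(0.4489 + 0.0081) = 0.676, with power Φ(2.488 - 1.645) = 80.0%. Power therefore stays between 80.0% and 80.6%.

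**The case against.** The strongest reply is that Criterion 18 already excludes anyone taking a listed drug, and that eligibility is checked at the Baseline Visit. Read strictly, the affected patient cannot pass. This stands as one reading, but the next sentence of the criterion, section 3.6.1 and Appendix 1 all date the prohibition from Day -7. A site relying on them would not be deviating. Two readings that give opposite answers for the same patient need reconciling.

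The second reply is that few patients are involved. Exclusion 8 names pulmonary hypertension as a disqualifying comorbidity, and Exclusion 12 removes recent unstable coronary disease. That is fair: it makes a small share likely, though the protocol gives no figure.

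The third concerns ABPM. The Schedule of Events carries a mark without a duration under Randomization in the ABPM row. Section 3.8.6 lists no recording at that visit, and section 3.9.2.1 lists only the monitor's return, so the mark is best read as the return.

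A reader might go further in three directions that the documents do not support:
- **That the primary UACR analysis is contaminated.** The protocol gives the Baseline Visit urines only an eligibility role (Inclusion 6b). It does not say which predose sample is the analysis baseline, a definition commonly left to the SAP, and a second set is collected inside the window.
- **That the 28-day stability rule for background therapy has the same defect.** Counting it back to Randomization is a stated design choice and contradicts nothing.
- **That the 14-day diltiazem entry conflicts with the 28-day stability of antihypertensives in Inclusion 5.** Inclusion and exclusion criteria are cumulative. A patient who fails either one is ineligible, so both can be applied together.

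**Conclusion.** The point holds for blood pressure. On 3 of the 7 permitted Baseline Visit days, the only pretreatment 24-hour ABPM and the final eligibility seated BP can be recorded while a same-pathway drug is still allowed. The undated opening of Criterion 18 is inconsistent with the dated text.

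The consequence is added noise and an understated within-arm BP fall in the affected patients. The rules apply before randomization and alike to all arms, so a biased comparison with placebo should not be inferred. No effect on the primary endpoint is shown, and the illustration above puts any loss of power at no more than 0.6 percentage points under its assumptions.

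The conclusion about dates rests on the protocol text alone. The size of the BP effect depends on how many patients stop a listed drug shortly before Day -7, which the protocol does not give. This is a worthwhile, inexpensive correction and does not threaten the trial's main result.

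**What to change.** Reconcile the opening of Exclusion 18 with its dated sentence, section 3.6.1 and Appendix 1, and reconcile all of them with the Baseline Visit timing, so that Baseline ABPM and seated BP fall within the prohibition period. This needs no new drug window, and none is proposed here. For patients who were taking a listed drug, the visit can be scheduled late enough within the existing Day -7 ± 3; Day -6 to Day -4 are clear of the boundary. Whether a current user at the Baseline Visit is excluded or may continue in screening is a clinical decision for the sponsor, but the text should give one answer.

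The cost is a short amendment to the eligibility and Baseline Visit text. For those patients there are fewer visit days to choose from and less time between the Baseline Visit and Randomization to review results. Sample size, power and the schedule for everyone else are unchanged.
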